9.3.1.3 Supportive Analyses

There will be no supportive analysis for the primary efficacy endpoint.

9.3.1.4 Sensitivity Analyses

MMRM based on Multiple Imputation (MI)

An underlying assumption of the MMRM method is that data are missing at random. To minimize the amount of missing data, subjects who prematurely discontinue study drug treatment will continue to complete all scheduled study visits for spirometry and other efficacy assessments.

To assess the impact of missing data and the assumption that data are missing at random, a multiple imputation algorithm will be used if at least 10% of the subjects have missing changes

in ppFEV₁ at Week 24 in any treatment group. Missing absolute change from baseline in ppFEV₁ assessments will be imputed starting from the first visit with missing values, for which all subsequent visits through Week 24 are also missing. For intermediate missing data, i.e., missing values that fall between two non-missing ones, it is reasonable to assume that they are missing at random and therefore will not be imputed. An MMRM analogous to that for the primary analysis of the primary endpoint will be applied to each imputed dataset and the relevant MI estimators will be reported. Details for the MI steps are presented in [Appendix D](#).

9.3.1.5 Subgroup Analysis

Subgroup analyses of the primary efficacy endpoint will be performed using a model similar to that of the primary analysis for each of the following subgroups.

- Age at Screening (<18, \geq 18 years)
- ppFEV₁ at baseline (< 70, \geq 70)
- Sex (male, female)

The MMRM used for the primary analysis will be used for the subgroup analysis, where the same model will be applied to each category of the subgroup. Note that for the subgroup analysis based on age, the covariate of age at screening (<18 versus \geq 18 years of age) from the MMRM will be removed. The adjusted means with 2-sided 95% CIs will be provided. Furthermore, estimated between group difference through Week 24 within a subgroup will also be presented in a forest plot. Note: Due to potential small sample size, the results from above mentioned subgroup analysis should be interpreted with caution.

9.3.2 Analysis of Secondary Endpoints

9.3.2.1 Definition of Variables

SwCl: the SwCl value for a given visit will be calculated as the mean of the non-missing sweat chloride measurements obtained on the left and right arms at that visit. If one of the two arm measurements at a time point is missing, the other will be used as the mean. A sweat volume \geq 15 μ L is required for an accurate determination of sweat chloride. Any results reported as having sweat volume <15 μ L or SwCl values reported as >160 mmol/L, will be considered missing. Any sweat chloride values reported as <10 mmol/L will be imputed as 10 mmol/L.

CFQ-R: The CFQ-R^{1,3,5} is a validated CF-specific instrument that measures quality-of-life domains. This study utilizes four different versions of CFQ-R:

CFQ-R for Children ages 6 to 11

CFQ-R for Children ages 12 and 13

CFQ-R for Adolescents and Adults (subjects 14 years and older)

CFQ-R for Parents/Caregivers (subjects 13 years and younger)

In all four versions, specific question belonging to a domain is scored 1, 2, 3, or 4. The CFQ-R domain score, e.g., physical domain score or respiratory domain score, is defined as a scaled score as follows:

$$\text{Scaled score for a domain} = 100 \times (\text{mean (scores of all questions in the domain)} - 1)/3,$$

where the score from a negatively phrased question is first reversed, i.e., reversed score = 5 – actual score, so that 1 always represents the worst condition and 4 the best condition. The (scaled) domain score ranges from 0 (worst condition) to 100 (best condition). The scaled score for a specific domain will not be calculated if more than half of the questions in the domain have missing scores.

The (scaled) domain score from the CFQ-R for Children ages 6 to 11, for Children ages 12 and 13 and for Adolescent and Adults will be pooled for the analysis purpose.

BMI: the BMI at each visit is calculated using the weight and height at each visit as follows:

$$BMI = \frac{\text{Weight (kg)}}{\text{Height}^2 (\text{m}^2)}$$

PEx: A PEx is defined as a new event or change in antibiotic therapy (IV, inhaled, or oral) for any 4 or more of the following signs/symptoms:

- Change in sputum
- New or increased hemoptysis
- Increased cough
- Increased dyspnea
- Malaise, fatigue, or lethargy
- Temperature above 38°C (equivalent to approximately 100.4°F)
- Anorexia or weight loss
- Sinus pain or tenderness
- Change in sinus discharge
- Change in PE of the chest
- Decrease in pulmonary function by 10%
- Radiographic changes indicative of pulmonary infection

The **PEx analysis period** will include the time from the first dose date of study drug in the treatment period until the last efficacy assessment. For subjects with a Week 24 Visit, the last efficacy assessment will be the Week 24 visit. For subjects who do not have a Week 24 Visit, the last efficacy assessment will be the earlier of Day 169 and the end of study participation.

The number of PEx through Week 24 is then defined as the total number of PEx for each treatment group during the PEx analysis period.

9.3.2.2 Analysis Method

Absolute change in SwCl from baseline through Week 24: The analysis of absolute change from baseline in SwCl through Week 24 will be based on an MMRM similar to the analysis of the primary endpoint above, with absolute change from baseline in SwCl at Day 15, Week 4, Week 8, Week 16, and Week 24 as the dependent variable.

The primary result obtained from the model will be the estimated treatment difference through Week 24, defined as the averaged treatment effects estimated at Week 4, Week 8, Week 16, and Week 24. The adjusted mean with a 2-sided 95% CI and a 2-sided *P* value will be provided.

The estimated within group change from baseline and treatment difference at each post-baseline visit, obtained from the model, will be provided. The estimated within group change and its SE at each post-baseline visit will also be plotted by treatment group. In addition, the post-baseline raw values and the absolute change from baseline at each post-baseline visit will be summarized descriptively (n, mean, SD, median, minimum, and maximum).

Absolute change from baseline in CFQ-R Respiratory Domain (RD) score through Week 24: Analysis of this domain will be based on an MMRM similar to the analysis of the primary efficacy variable. Data obtained from Week 4, Week 8, Week 16, and Week 24 Visits will be included in the model to estimate the treatment effect through Week 24. Plot and summary tables similar to those for ppFEV₁ and SwCl will be provided.

Absolute change from baseline in BMI at Week 24: Analysis of this variable will be based on an MMRM similar to the analysis of the primary efficacy variable. Data obtained from Day 15, Week 4, Week 8, Week 16, and Week 24 Visits will be included in the model. Plot and summary tables similar to those for ppFEV₁ and SwCl will be provided.

Absolute change from baseline in weight at Week 24: Analysis of this variable will be based on an MMRM similar to the analysis of the primary efficacy variable. Data obtained from Day 15, Week 4, Week 8, Week 16, and Week 24 Visits will be included in the model. Plot and summary tables similar to those for ppFEV₁ and SwCl will be provided.

Number of PEx through Week 24: The number of PEx during the PEx analysis period will be performed using a negative binomial regression model with a fixed effect for treatment, as well as continuous baseline ppFEV₁, age at screening (<18 versus ≥18 years of age) and mutation group (contains ≥ 1 RF-like mutation versus does not contain an RF-like mutation) as covariates. The logarithm of the subject-specific PEx analysis period duration (in years) will be treated as the offset in the model. The estimated rate ratio and the associated 2-sided 95% CI and 2-sided *p*-value will be provided. If model does not converge, alternative models (e.g., a Poisson model with the same covariates) might be used instead.

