12.3.3 Efficacy and Pharmacodynamics Analysis

12.3.3.1 Analysis of Primary Efficacy Endpoint

The primary endpoint is the absolute change from baseline in ppFEV₁ through Week 24.

The primary analysis will be based on a mixed-effects model for repeated measures (MMRM). The model will include the absolute change from baseline in ppFEV₁ at Day 15, Week 4, Week 8, Week 16, and Week 24 as the dependent variable; treatment group, visit, and treatment-by-visit as fixed effects; additional covariates will be included as appropriate and details will be specified in the SAP. The model will be estimated using restricted maximum likelihood. Denominator degrees of freedom for the F test for fixed effects will be estimated using the Kenward-Roger approximation. An unstructured covariance structure will be used to model the within-subject errors. If the model estimation does not converge, a compound symmetry covariance structure will be used instead. Conditional on the observed data and covariates, missing data will be assumed to be missing at random; consequently, no imputation of missing data will be performed.

The primary result obtained from the model will be the estimated treatment difference through Week 24. The adjusted mean with a 2-sided 95% CI and a 2-sided *P* value will be provided.

Furthermore, the adjusted mean and treatment difference at each post-baseline visit will also be provided, obtained from the model.

Sensitivity analyses for handling missing data will be described in the SAP.

Supportive analyses and subgroup analyses of the primary efficacy variable will also be described in the SAP.

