4 INTRODUCTION

This SAP for the final analysis is based on the most recent approved clinical study protocol (CSP), electronic case report form (eCRF), and eCRF completion guidelines.

This SAP (Methods) documents the planned statistical analyses of efficacy endpoints and safety endpoints for the final analysis. Analyses related to sweat chloride will be documented in this SAP. Other PK and PD analyses will be documented separately in the CPAP for the study.

This SAP (Methods) will be finalized and approved prior to data lock and treatment unblinding. Any revisions to the approved SAP prior to data lock will be documented and approved in an amendment to the SAP and deviations from the approved SAP after data lock will be summarized in the CSR.

The Vertex Biometrics Department will perform the statistical analysis for the final analysis and prepare the analysis package for the final analysis; SAS (Version 9.4 or higher) will be used to generate all statistical outputs (tables, figures, listings, and datasets).

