7.3 Randomization

Subjects will be randomized 2:1 (ELX/TEZ/IVA group: placebo group). Randomization will be stratified based on ppFEV₁ determined during the Screening Period (<70 versus \geq 70), age at the Screening Visit (<18 years old versus \geq 18 years old) and *CFTR* mutation group (contains \geq 1 RF-like mutation versus does not contain an RF-like mutation).

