9.3.1.2 Primary Analysis

The primary analysis will be performed using a MMRM with change from baseline at Day 15, Week 4, Week 8, Week 16, and Week 24 as the dependent variable. The model will include treatment group, visit, and treatment by visit interaction as fixed effects, with continuous baseline ppFEV₁, age at screening (<18 versus \geq 18 years of age) and mutation group (contains \geq 1 RF-like mutation versus does not contain an RF-like mutation) as covariates. The model will be estimated using restricted maximum likelihood. Denominator degrees of freedom for the *F*-test for fixed effects will be estimated using the Kenward-Roger approximation². An unstructured covariance structure will be used to model the within-subject errors. If the model estimation does not converge, a compound symmetry covariance structure will be used instead. Conditional on the observed data and covariates, missing data will be assumed to be missing at random.

The primary result obtained from the model will be the estimated treatment difference through Week 24, defined as the averaged treatment effects estimated at Week 4, Week 8, Week 16, and Week 24. The adjusted means with 2-sided 95% CIs and 2-sided *P* value will be provided. Furthermore, the treatment difference at each post-baseline visit obtained from the model will also be provided.

The estimated within group change from baseline and treatment difference at each post-baseline visit, obtained from the model, will be provided. The estimated within group change and its SE at each post-baseline visit will also be plotted by treatment group. In addition, the post-baseline raw values and the absolute change from baseline at each post-baseline visit will be summarized descriptively (n, mean, SD, median, minimum, and maximum).

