9.3.3.2 Analysis Method

Absolute change from baseline in BMI z-score at Week 24 (for subjects ≤ 20 years of age at Baseline): Analysis of this variable will be based on an MMRM similar to the analysis of the primary efficacy variable, excluding the covariate of age at screening (<18 versus ≥ 18 years of age), for subjects ≤ 20 years of age at Baseline. Data obtained from Day 15, Week 4, Week 8, Week 16, and Week 24 Visits will be included in the model. Plot and summary tables similar to those for ppFEV₁ and SwCl will be provided.

Absolute change from baseline in Weight z-score at Week 24 (for subjects ≤ 20 years of age at Baseline): Analysis of this variable will be based on an MMRM similar to the analysis of the primary efficacy variable, excluding the covariate of age at screening (<18 versus ≥ 18 years of age), for subjects ≤ 20 years of age at Baseline. Data obtained from Day 15, Week 4, Week 8, Week 16, and Week 24 Visits will be included in the model. Plot and summary tables similar to those for ppFEV₁ and SwCl will be provided.

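### The covariates of the SwCl, CFQ-R RD, BMI and weight MMRMs are not listed; read literally, the models omit each endpoint's own baseline, which can widen confidence intervals for no benefit

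*SAP*

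**What the plan says.** For the primary endpoint, Protocol 12.3.3.1 states that "additional covariates will be included as appropriate and details will be specified in the SAP". SAP 9.3.1.2 supplies them: the model is fitted "with continuous baseline ppFEV₁, age at screening" (under 18 versus 18 and over) and mutation group.

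For the secondary endpoints, Protocol 12.3.3.2 calls the four continuous models similar to the primary one. SAP 9.3.2.2 does the same: the sweat chloride (SwCl) analysis "will be based on an MMRM similar to the analysis of the primary endpoint above, with absolute change from baseline in SwCl" at the scheduled visits. CFQ-R RD, BMI and weight get parallel sentences. Outcome and visits are given; covariates are not.

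Covariates are mentioned in three other analyses:

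- SAP 9.3.3.2 (BMI and weight z-scores) uses a similar MMRM "excluding the covariate of age at screening". It mentions no other change to the list.
- SAP 9.3.1.5 (subgroups of the primary endpoint) has the sentence beginning "Note that for the subgroup analysis based on age, the covariate of age at screening", which removes that term only.
- SAP 9.3.2.2 analyses exacerbations with a "negative binomial regression model with a fixed effect for treatment, as well as continuous baseline ppFEV₁, age at screening" and mutation group.

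No section places baseline SwCl, CFQ-R RD, BMI or weight in a model.

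**The concern.** In the primary model, baseline ppFEV₁ does two jobs. It is the endpoint's own baseline, and it stands in for a stratification factor (SAP 7.3: "Randomization will be stratified based on ppFEV₁ determined during the Screening Period"). If the list is carried unchanged to another endpoint, only the second job survives. A change score is usually correlated with its own baseline, so leaving that baseline out leaves explainable variance in the residual.

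SwCl, CFQ-R RD, BMI and weight are the first four secondary tests in the fixed sequence of SAP 9.3.2.3, where a failed step stops all later ones. At least three models fit the present wording: ppFEV₁ only, own baseline only, or both. The model behind each formally tested result should be fixed in advance, and it should use a baseline value that the trial already collects.

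**Working it through.** **The plan's own figure.** SAP 7.2 states about 90% power for ppFEV₁ (difference 4.0, SD 9, 180 versus 90, 10% dropout, two-sided 0.05). Evaluable subjects: 0.9 × 180 = 162 and 0.9 × 90 = 81, total 243. The noncentrality is 4 / (9 × √(1/162 + 1/81)) = 3.27; with 241 df, power is 90.2%. The figure reproduces, but it concerns ppFEV₁ only. The documents give no SD, effect size, correlation or power for the secondary endpoints.

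**Assumed inputs.** ρ is the common correlation between baseline and each visit, and between visits, given the three existing covariates. k is the follow-up SD divided by the baseline SD. Neither is in the documents.

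**Formulas.** Let r² be the share of the variance of change explained by the endpoint's own baseline.

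- Average of four visits: r² = (ρk − 1)² / [k²(1 + 3ρ)/4 + 1 − 2ρk]. The SAP defines the SwCl effect this way (Weeks 4, 8, 16 and 24), and CFQ-R RD uses the same four visits.
- One visit (BMI and weight at Week 24): r² = (ρk − 1)² / [k² + 1 − 2ρk].
- Widening of the interval when the own baseline is omitted: 1/√(1 − r²) − 1.

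**Worked cases.** Four visits, ρ = 0.7, k = 1: r² = 0.09/0.375 = 0.240, and 1/√0.760 − 1 = 14.7%. With k = 0.9: r² = 0.1369/0.36775 = 0.372, and the widening is 26.2%. One visit, ρ = 0.95, k = 1: r² = 0.0025/0.10 = 0.025, and the widening is 1.3%.

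| Four-visit average | ρ = 0.9 | ρ = 0.7 | ρ = 0.55 |
|---|---|---|---|
| k = 0.9 | 17.8% | 26.2% | 36.9% |
| k = 1.0 | 4.3% | 14.7% | 25.0% |
| k = 1.1 | 0.04% | 7.4% | 16.5% |

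| Week 24 only | ρ = 0.95 | ρ = 0.98 |
|---|---|---|
| k = 0.95 | 5.3% | 6.5% |
| k = 1.0 | 1.3% | 0.5% |
| k = 1.1 | 0.9% | 6.2% |

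The gain is exactly zero when k = 1/ρ and grows as k moves away from that value in either direction.

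**Simulation check.** With 162 versus 81 subjects, 4,000 runs and the three existing covariates in both models, the ratio of standard errors (without versus with own baseline) at k = 1 was 1.040, 1.145 and 1.248 for four visits (ρ = 0.9, 0.7, 0.55), and 1.011 and 1.003 for one visit (ρ = 0.95, 0.98). Mean estimates were within 0.003 SD of the truth in both models. A second simulation (2,000 runs per setting) gave type I error of 4.3% to 5.6% with or without the own baseline, consistent with 5%.

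**Cost of adding the term.** With 243 subjects and five mean parameters (intercept, treatment, three covariates), residual df fall from 238 to 237. If the own baseline predicts nothing, the standard error rises by √(238/237) − 1 = 0.21%.

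**The case against.** The strongest reply is that the SAP does not say the own baseline is left out. In the primary model, baseline ppFEV₁ is the own baseline, so a similar model for SwCl may just as naturally mean baseline SwCl. Two of the apparent supports for the literal reading are weak. The age-subgroup note concerns ppFEV₁ itself, where no swap could arise. The exacerbation model is a count model with no baseline counterpart defined, so its covariates had to be written out. The match with the stratification factors is also only partial, because the SAP replaces the screening ppFEV₁ category with a continuous baseline. All of this stands. What remains for the literal reading is that 9.3.1.2 holds the only MMRM list, and that 9.3.3.2, which adapts it to endpoints other than ppFEV₁, drops age and mentions no baseline change. That makes omission the literal result, not an established intention.

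A reader might infer more than this, and the documents do not support it:

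- *That the secondary results would be biased or the type I error inflated.* Under randomization they would not be, and the simulations showed neither. With missing data, validity also rests on the missing-at-random assumption that the SAP already makes.
- *That the secondary tests lose a stated amount of power.* The 90% benchmark belongs to ppFEV₁ alone.
- *That SwCl and CFQ-R RD are hurt most and BMI and weight hardly at all.* This depends on the inputs chosen: at k = 1.1 the loss is 0.04% for a four-visit average with ρ = 0.9, but 6.2% for a single visit with ρ = 0.98.
- *That the SAP is certainly still open.* Section 4 says "This SAP (Methods) will be finalized and approved prior to data lock and treatment unblinding", but the public text does not show whether approval has been given.

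**Conclusion.** The covariates of the four secondary MMRMs are not stated in either document. Followed literally, the SAP fits them with baseline ppFEV₁ and without the endpoint's own baseline. That model is valid but may give wider intervals than necessary.

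The cost cannot be fixed from the documents. In the cases shown it runs from practically nothing to about 37% for a four-visit average, and from about 0.5% to 6.5% for the Week 24 endpoints. These figures assume compound symmetry and the listed correlations and SD ratios. They illustrate the size and are not bounds. They apply only if the literal reading is the intended one; if the sponsor already means to adjust for the own baseline, what remains is a gap in pre-specification that the same sentence closes. No ranking of endpoints and no loss of power is claimed. The point is a free improvement that should be made.

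**What to change.** Before data lock and unblinding, add to SAP 9.3.2.2 (for the four MMRMs) and 9.3.4.2 (non-respiratory CFQ-R domains): *The covariates are the continuous baseline value of the endpoint analysed, continuous baseline ppFEV₁, age at screening (<18 versus ≥18 years) and mutation group.* In 9.3.3.2 (z-scores) use the same list without age. Keeping baseline ppFEV₁ preserves the adjustment linked to a stratification factor.

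The cost is one sentence and about one model degree of freedom per endpoint, or 0.2% in standard error in the worst case worked above. No new data are needed and no subject is lost, because anyone with a change score has the baseline value. If the SAP is already approved, Section 4 requires a documented and approved amendment.

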9.3.2.3 Multiplicity Adjustment

The secondary endpoints will be formally tested at an alpha of 0.05 at the final analysis when all subjects complete study participation. A hierarchical testing procedure will be used to control the type I error rate for the multiple secondary endpoints tested at an alpha of 0.05. For a test at any step to be considered statistically significant within the testing hierarchy, it must be statistically significant, and all previous tests (if any) within the hierarchy must be statistically significant at the 0.05 level. The testing order of the secondary endpoints is as follows:

1. First secondary endpoint: Absolute change in SwCl from baseline through Week 24
2. Second secondary endpoint: Absolute change in CFQ-R respiratory domain from baseline through Week 24
3. Third secondary endpoint: Absolute change in BMI from baseline at Week 24
4. Fourth secondary endpoint: Absolute change in weight from baseline at Week 24

5. Fifth secondary endpoint: Number of PEx through Week 24

9.3.3 Analysis of Other Endpoints

9.3.3.1 Definition of Variables

BMI z-score: the BMI score, adjusted for age and sex, will be referred to as BMI-for-age z-score (BMI z-score). The BMI z-score will be calculated by using Centers for Disease Control and Prevention (CDC) growth charts⁷, with the age (in months) used for the calculation defined in [Appendix A](#).

Weight z-score: weight, adjusted for age and sex, will be referred to as weight-for-age z-score (Weight z-score). The Weight z-score will be calculated by using Centers for Disease Control and Prevention (CDC) growth charts⁷, with the age (in months) used for the calculation defined in [Appendix A](#).

